#### 8.1.5. Visual Acuity Response Endpoints

Binocular DCNVA response endpoints are defined as follows:

- Binocular DCNVA 2-line gain response: having an increase in DCNVA of 10 letters
  (2 lines) or more from baseline and having no decrease in BCDVA of more than 5 letters
  (1 line). That is, change from baseline in DCNVA ≥ 10 letters and change from baseline
  in BCDVA ≥ -5 letters.

#### The three Study Eye DCNVA response endpoints are defined similarly.

For a response endpoint, the response rate at a given post-baseline visit is calculated as the proportion of subjects who met the response criterion at that visit.

#### 8.1.6. Treatment Satisfactory Response Endpoints

The treatment satisfactory response endpoint is defined as having the response of either 'Satisfactory' or 'Very Satisfactory' when asked to rate the overall satisfactory with the treatment under Patient Global Rating of Treatment questionnaire.

#### 8.1.7. Refractive Status and Manifest Refraction Spherical Equivalent Endpoint

Manifest refraction spherical equivalent (MRSE) is calculated by adding the spherical power with half of the cylindrical power, where spherical and cylindrical power are measured from the subjective refraction test.

Based on the MRSE, a refractive status of an eye will be defined as follows:

- Myopia: MRSE < -0.25D
- Emmetropia:  $-0.25D \le MRSE \le +0.25D$
- Hyperopia: MRSE > +0.25D

#### 8.1.8. Lens and Corneal Elasticity

Five parameters for lens elasticity are (1) width of the bottom plateau, (2) width of the top plateau, (3) height of the plateau, (4) slope of the anterior cortex, and (5) slope of the posterior cortex. Lens elasticity will be measured in triplicate on each eye at each visit. Measurement values across multiple scans of each parameter will be averaged and used for the analysis. Any unsuccess scans whose all 5 parameters are zeros will be excluded before the averaging calculation.

Corneal elasticity will be measured in duplicate on each eye at Baseline and Month 2 visit. The average value of corneal elasticity across multiple scans will be used for analysis.

# 8.2. Analyses of Primary Endpoint

### 8.2.1. Historical Control Data

Searching the clinicaltrials.gov database for presbyopia clinical studies with pharmacological treatment with the exposure duration of 2 months or longer, the study team identified three studies with similar study populations and inclusion/exclusion criteria. Out of three studies, only one (NCT02516306) has reported the study results (Korenfeld, 2011) with the same endpoint as this study's primary endpoint. Based on the historical data of 23 subjects in the control group, the estimated mean  $\pm$  standard deviation of the change from baseline in binocular DCNVA at Month 2 is reported as -0.085  $\pm$  0.087 logMAR, or 4.25  $\pm$  4.35 EDTRS letters read.

A power prior with a power parameter w, presenting the prior knowledge learned from a study with  $n_0$  subjects, will be derived based on the estimated mean  $\hat{\mu}_0$ , and standard deviation  $s_0$  as follows:

$$\mu \sim \mathrm{N}\left(\widehat{\mu_0}, \frac{s_0^2}{w \cdot n_0}\right),$$

where  $\mu$  is the mean change from baseline in binocular DCNVA, N( $\cdot$ ,  $\cdot$ ) denotes the normal distribution with the first and second parameter indicating mean and variance, respectively. Hence, the effective sample size borrowing from the historical control data will be  $w \cdot n_0$ .

### 8.2.2. Primary Analyses

The primary efficacy endpoint is the change from Baseline (Day 1) in binocular DCNVA at Month 2 (Visit 6).

For comparison of 0.1% STN1013600 vs Placebo and of 0.3% STN1013600 vs Placebo, the primary endpoint will be evaluated under the Bayesian framework in accordance with the following null (versus alternative) hypothesis:

$$H_0: \mu_T \le \mu_C$$
versus
$$H_A: \mu_T > \mu_C$$

where  $\mu_T$  and  $\mu_C$  is the mean value of change from baseline binocular DCNVA at Month 2 of the treatment group and the control group, respectively.

For the primary analysis, a power prior with power parameter w will be used for the control group mean and a non-informative prior,  $p(\mu_T) \propto 1$ , for the treatment group mean. Based on the posterior means and variances for treatment and control groups, the probability of (Treatment mean – Control mean > 0) given the data i.e.,  $P(\mu_T - \mu_C > 0 \mid \text{Data})$  will be calculated. The null hypothesis H0 will be rejected and the efficacy of the treatment will be declared when  $P(\mu_T - \mu_C > 0 \mid \text{Data}) > 0.95$ . The details for historical data borrowing analysis are in Section 12.2.

#### 8.2.3. Sensitivity Analyses

To assess the robustness of results from the primary analysis in the presence of prior-data conflict (i.e., the mean of historical data is different from the observed mean of the placebo arm), a mixed-effect model for repeated measures (MMRM) will be performed in observed cases up to Month 3 for the primary endpoint. The model will include treatment, analysis visit, and treatment-by-visit interaction as fixed effects, and baseline binocular DCNVA at baseline as a covariate, and subject as a random effect. The denominator degrees of freedom for fixed effects will be estimated using the Kenward-Roger approximation. An unstructured covariance matrix will be used to model the within-subject errors.

If there are convergence issues, covariance matrix structures other than unstructured will be tried in the following order: (1) heterogeneous Toeplitz (TOEPH), (2) heterogeneous autoregressive of order 1 (ARH(1)), (3) heterogeneous compound symmetry (CSH), and (4) compound symmetry (CS). The first covariance structure that converges will be used for this sensitivity analysis. Least squares mean change from baseline at Month 2 and differences between least squares treatment arm means and associated 90% confidence intervals will be reported.

In addition, the following sensitivity analyses will be performed to assess the robustness of the results from the primary analysis:

• The primary analysis will be repeated on the PP Population.

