#### **Treatment Period (2 months):**

At Visit 2 (Baseline), approximately 75 eligible subjects will be randomized to receive either 0.1% STN1013600 ophthalmic solution BID or 0.3% STN1013600 ophthalmic solution BID or Placebo BID in a 2:2:1 ratio. Subjects will be treated for 2 months with scheduled assessment visits at Visit 2 (Baseline), Visit 3 (Day 7), Visit 4 (Day 14), Visit 5 (Month 1), and Visit 6 (Month 2).

At Visit 2 (Baseline), subjects will administer their first dose of study medication (study eye drops) as per their assigned/randomized study treatment at  $20:00 (\pm 60 \text{ min})$ . The next day

(Day 2), subjects will subsequently dose with their assigned study medication at  $08:00 \& 20:00 (\pm 60 \text{ min})$  and continue dosing through Visit 6 (Month 2).

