### 8.3. Analyses of Secondary Efficacy Endpoints

#### 8.3.1. Analyses of Continuous Secondary Endpoints

The following secondary endpoints will be analyzed using MMRM on observed cases up to Month 3:

- Mean change from baseline in Study Eye DCNVA at all visits
- Mean change from baseline in Binocular DCNVA at all visits
- Mean change from baseline in Rasch score at Month 2 and Month 3 as measured by Near Activity Visual Questionnaire (NAVQ)
- Mean change from baseline in the NAVQ overall satisfactory rating of near vision at Month 2 and at Month 3

For the analysis of the above secondary endpoints, the MMRM model will include treatment, visit, and treatment-by-visit as fixed effects, baseline as covariate and subject as random effect. The denominator degrees of freedom for fixed effects will be estimated using the Kenward-Roger approximation. An unstructured covariance matrix will be used to model the within-subject errors. When non-convergence issue arises, covariance structure in the following order will be tried: (1) heterogeneous Toeplitz (TOEPH), (2) heterogeneous autoregressive of order

1 (ARH(1)), (3) heterogeneous compound symmetry (CSH), and (4) compound symmetry (CS). The first covariance structure that converges will be used for the analysis.

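### SAP 8.2.3 and 8.3.1 pair a random subject effect with an unstructured covariance; the redundant variance could start the covariance fallback without cause (low severity)

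*SAP*

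**What the plan says.** SAP 8.2.3 sets out an MMRM to test the primary result against conflict between the historical and the concurrent controls. It "will be performed in observed cases up to Month 3 for the primary endpoint". Besides the fixed effects, the model has "and baseline binocular DCNVA at baseline as a covariate, and subject as a random effect". The same paragraph adds: "An unstructured covariance matrix will be used to model the within-subject errors". On inference: "The denominator degrees of freedom for fixed effects will be estimated using the Kenward-Roger approximation".

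The fallback rule reads: "If there are convergence issues, covariance matrix structures other than unstructured will be tried in the following order", followed by TOEPH, ARH(1), CSH and CS. Then: "The first covariance structure that converges will be used for this sensitivity analysis". No step takes the random effect out before the structure is changed, and the SAP does not say which software messages count as a convergence issue.

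SAP 8.3.1 uses the same model for study-eye DCNVA, binocular DCNVA and the two NAVQ scores, with "baseline as covariate and subject as random effect", an unstructured matrix, Kenward-Roger degrees of freedom and the same fallback order.

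**The concern.** An unstructured matrix already gives every visit its own variance and every pair of visits its own covariance. A random subject intercept adds one constant to all of these elements, so the data cannot tell the two sources apart. Read literally, the specified model has one covariance parameter too many.

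This matters because the SAP ties the choice of covariance structure to convergence. A singular Hessian or a non-positive-definite G matrix, caused only by the redundant parameter, could be read as the trigger. The analysis would then leave the unstructured model for a reason unrelated to the data. Kenward-Roger is exposed as well, because it uses the inverse of the information matrix of the covariance parameters, and that matrix is singular here. At stake are the standard errors and 90% confidence intervals of the sensitivity analysis and of the continuous secondary endpoints.

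**Working it through.** The SAP gives no figure on this point to reproduce, so the check is structural.

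**Inputs from the SAP.** DCNVA has k = 5 post-baseline visits: Day 7, Day 14, Month 1 and Month 2 (Section 3.1), and Month 3, because the model runs to Month 3 (8.2.3). NAVQ has k = 2: Month 2 and Month 3 (8.3.1). The arms have 30, 30 and 15 subjects (3.3).

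**Step 1: redundancy.** The covariance of one subject's visits is V = σ_b²·J + R, where J is a matrix of ones and R the residual matrix. If R is unstructured, then for any c that keeps the new residual matrix positive definite, (σ_b² + c, R − c·J) gives the same V. V has k(k+1)/2 distinct elements, and the model has k(k+1)/2 + 1 covariance parameters.

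- DCNVA: 5·6/2 = 15 elements, 16 parameters.
- NAVQ: 2·3/2 = 3 elements, 4 parameters.

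**Step 2: rank.** The expected information has elements ½·tr(V⁻¹ ∂V_i V⁻¹ ∂V_j). Its rank, with the random intercept kept in every structure, is:

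| Structure | k = 5, unequal visit SDs | k = 5, equal visit SDs | k = 2 |
|---|---|---|---|
| UN | 15 of 16 | 15 of 16 | 3 of 4 |
| TOEPH | 10 of 10 | 9 of 10 | 3 of 4 |
| ARH(1) | 7 of 7 | 7 of 7 | 3 of 4 |
| CSH | 7 of 7 | 6 of 7 | 3 of 4 |
| CS | 2 of 3 | 2 of 3 | 2 of 3 |

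The unequal SDs were assumed as 5.0, 5.4, 5.8, 6.2 and 6.0 letters. The full ranks of TOEPH, ARH(1) and CSH also hold at 4, 4.5, 5, 6 and 6 letters with correlation 0.5.

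**Step 3: what stays identified.** One data set was simulated (15/30/30 subjects, five visits, the first SD pattern above, AR(1) correlation 0.6; the SDs and the correlation are assumptions). The unstructured V was estimated by REML, and variance was then moved between σ_b² and R = V − σ_b²·J. With σ_b² at 0, 2.34, 4.67 and 8.41, R stayed positive definite. Each time −2 REML log-likelihood was 1454.19, the Month 2 difference 5.793 letters and its standard error 1.747. The likelihood is flat along this line and the reported results do not move. The value σ_b² = 0 is the ordinary unstructured MMRM.

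**Step 4: size of an unneeded fallback.** In the same data set, with the structures fitted without the random intercept, the standard error of the Month 2 difference was:

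| Structure | SE | Ratio to UN |
|---|---|---|
| UN | 1.747 | 1.00 |
| TOEPH | 1.786 | 1.02 |
| ARH(1) | 1.795 | 1.03 |
| CSH | 1.749 | 1.00 |
| CS | 1.497 | 0.86 |

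A direct calculation for CS with assumed SDs of 4, 4.5, 5, 6 and 6 letters: the pooled variance is (16 + 20.25 + 25 + 36 + 36)/5 = 26.65 and the pooled SD 5.16. Against 6 at Month 2 the ratio is 0.86, so the standard error is about 14% too small. A nominal 90% interval then covers 2Φ(1.645 × 0.86) − 1, about 84%.

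The size depends on the SD pattern. The SDs used to generate the simulated data give a pooled variance of 162.24/5 = 32.45, a pooled SD of 5.70 and a ratio to 6.2 of 0.92, or about 8%.

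**Step 5: NAVQ.** With two visits, TOEPH, ARH(1) and CSH each consist of two variances and one correlation. That is the same marginal model as UN, so only CS would change the result.

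**The case against.** The strongest reply is that the wording is merely loose. The model is called an MMRM, one matrix is named for the within-subject errors, and the fallback changes only that matrix. The random subject effect may be meant only to identify the subject within which visits repeat. That is plausible, and the remedy would then be purely editorial. But the pair appears in two sections, and nothing in the text reviewed says that the phrase has this narrower meaning.

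A second reply is that no failed fit has been shown. This stands. Failure is possible but not certain.

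A reader might infer three stronger points that the documents do not support.

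- **That the intervals will be materially too narrow.** The SAP keeps the first structure that converges. In the five-visit model TOEPH, ARH(1) and CSH are of full rank when visit SDs differ, and ARH(1) is so even when they are equal. Redundancy alone therefore does not carry the fallback to CS. The 2 to 3% changes at TOEPH and ARH(1) were towards wider intervals.
- **That NAVQ has no usable model.** Every listed structure is over-parameterised once the random effect is added. Only the split of variance is unidentified, however, and not the total covariance that determines the results.
- **That this MMRM is the sole look at the primary endpoint without historical controls.** SAP Section 5 also plans descriptive summaries of all measures, and the borrowing details assigned to Section 12.2 are not in the text reviewed.

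**Conclusion.** The point holds as a specification error of low severity. As written, the random-intercept variance is not identifiable beside the unstructured matrix, whatever the data. The total covariance, the least squares means and their model-based standard errors are identified. The exposure is a fallback started by the redundant parameter, and a Kenward-Roger calculation that rests on a singular matrix.

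If such a fallback occurred with five visits and unequal SDs, a change in standard error of about 2 to 3% is the realistic size. It comes from one simulated data set with assumed SDs and correlation. The figure of about 14% needs the analysis to reach CS and visit SDs that differ enough; it is a worst case and not an expectation.

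The Bayesian primary analysis does not use this model. SAP 5.4 plans one hypothesis test, for the primary endpoint, so no confirmatory claim depends on the MMRM.

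**What to change.** In SAP 8.2.3 and 8.3.1, delete the random subject effect. State that within-subject correlation is modelled only through the residual covariance, with visit as the repeated factor within subject, an unstructured matrix and Kenward-Roger degrees of freedom. Apply the fallback order only to that model.

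The cost is one phrase removed and one sentence added in each of two sections, with no change to data collection. Nothing is lost: in the simulated data the fit without the random effect had the same likelihood, estimate and standard error as the fit with it.

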### 8.3. Analyses of Secondary Efficacy Endpoints

#### 8.3.1. Analyses of Continuous Secondary Endpoints

The following secondary endpoints will be analyzed using MMRM on observed cases up to Month 3:

- Mean change from baseline in Study Eye DCNVA at all visits
- Mean change from baseline in Binocular DCNVA at all visits
- Mean change from baseline in Rasch score at Month 2 and Month 3 as measured by Near Activity Visual Questionnaire (NAVQ)
- Mean change from baseline in the NAVQ overall satisfactory rating of near vision at Month 2 and at Month 3

For the analysis of the above secondary endpoints, the MMRM model will include treatment, visit, and treatment-by-visit as fixed effects, baseline as covariate and subject as random effect. The denominator degrees of freedom for fixed effects will be estimated using the Kenward-Roger approximation. An unstructured covariance matrix will be used to model the within-subject errors. When non-convergence issue arises, covariance structure in the following order will be tried: (1) heterogeneous Toeplitz (TOEPH), (2) heterogeneous autoregressive of order

1 (ARH(1)), (3) heterogeneous compound symmetry (CSH), and (4) compound symmetry (CS). The first covariance structure that converges will be used for the analysis.

### 8.3.2. Analyses of Binary Secondary Endpoints

The following binary secondary endpoints will be summarized descriptively:

- Having Binocular DCNVA 1/2/3-line gain from baseline at each visit
- Having Study Eye DCNVA 1/2/3-line gain from baseline at each visit
- Proportion of subjects with treatment satisfactory assessed by Patient Global Rating of Treatment at Month 2

The responder rates will be tabulated using frequencies and percentages based on observed cases.

For exploratory purposes, comparison between 0.1% STN1013600 vs Placebo and between 0.3% STN1013600 vs Placebo in response rate will be performed using the Fisher's Exact test for a 2x2 contingency table.

## 8.4. Subgroup Analyses

The homogeneity of treatment effects among prospectively defined subgroups will be assessed via descriptive statistics of the change from baseline in Binocular DCNVA by analysis visit for the following subgroups:

- Age (47-50 or 51-55 years)
- Sex (males or females)
- Race (White or non-White)
- Baseline Binocular DCNVA (< 60 or  $\ge$  60 ETDRS letters)
- Baseline refractive status of the Study Eye (Myopia or Emmetropia or Hyperopia)

Other subgroup analyses may be performed as deemed necessary.

### 8.5. Exploratory Analyses

# 9. SAFETY ANALYSES

# 9.1. Safety-Related Definitions

#### 9.1.1. Adverse Event

Under Protocol 101360002IN, an AE is defined as any *on*-study untoward medical occurrence (e.g., sign, symptom, disease, syndrome, intercurrent illness) that occurs in a study subject, regardless of the suspected cause and regardless of the timing of the study medication administration. An on-study AE can occur any time after the date of informed consent through the last study visit. An AE will be considered as *treatment-emergent* if the AE occurred on or after the treatment start date up to 8 days after treatment end date (or the last study visit). Treatment-emergent AEs (TEAEs) are a subset of on-study AEs. Both on-study and TEAEs will be collected, but only TEAEs will be tabulated.

The severity of each AE will be graded by the Clinical Investigator as Mild, Moderate, or Severe. AEs will also be rated by the Investigator as to their causality/relationship to the study drug.

Each AE will be classified into a system organ class (SOC) and coded to a preferred term (PT) using Medical Dictionary for Regulatory Activities (MedDRA), version 25.1 published in September 2022.

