8.3.1. Time Period and Frequency for Collecting AE and SAE Information

All AEs will be collected from the signing of the Informed Consent Form (ICF) until subject withdrawal or the scheduled exit visit. (Note: Although AEs will be monitored for and collected prior to IP administration, the statistical data analysis will determine and summarize treatment-emergent AEs, *i.e.*, those AEs that began or worsened in severity after the first IP administration.)

All SAEs will be recorded and reported to the sponsor or designee immediately and under no circumstance should this exceed 24 hours, as indicated in Section 10.3. The investigator will submit any updated SAE data to the sponsor within 24 hours of it being available.

Investigators are not obligated to actively seek AE or SAE after conclusion of the study participation. However, if the investigator learns of any SAE, including a death, at any time after

a participant has been discharged from the study, and he/she considers the event to be reasonably related to the study intervention or study participation, the investigator must promptly notify the sponsor.

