### Figure 1: Study Design Diagram

\* On Day 1, subject should administer 1 dose of assigned medication after study visit at  $20:00 \pm 60$  min. BID dosing starts from Day 2 through Month 2.

This study will consist of a Screening Period of up to 15 days, followed by a 2-month Treatment Period and subsequently a 1-month Treatment-free follow-up Period.

At Visit 1 (Screening), subjects will be screened against the inclusion and exclusion criteria and if subject meets all eligibility criteria, subjects will proceed to Visit 2 (Baseline).

Per study design, subjects who qualify per eligibility criteria will be treated bilaterally (both eyes).

The study eye will be the eye that qualifies with the worse DCNVA per eligibility criteria at Visit 2. If both eyes have the same DCNVA, the right eye will be designated as the study eye.

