#### Table 2: Assessment Schedule (Continued)

a Informed Consent Form must be signed and dated before study procedures are performed.

b NAVQ and SANDE questionnaires are to be performed at the beginning of the study visit, in the order reflected on Schedule of Assessments Table.

c During screening, cycloplegic refraction (objective refraction with dilation) should be performed; At visit 7 objective refraction can be performed with or without cycloplegia.

d DCNVA, and BCDVA assessments should be performed on OD, OS, and OU.

g Dilated ophthalmoscopy required at Screening and Exit visits.

h Urine pregnancy test (women of childbearing potential only) may be repeated at each visit as per request of IRB/IECs or at the Investigator's discretion.

i Only patients fulfilling eligibility criteria will be enrolled and receive the study medication.

j Dispense medication compliance diaries with when study medication is dispensed and instruct subjects on the proper completion of the diary. Collect paper diaries at specified visits and review for accuracy and completeness. Dosing for randomized subjects on Visit 2 (Day 1/Baseline) is after the study visit in the evening  $(20:00 \pm 60 \text{ min})$ , and Day 2 through Month 2 is daily BID  $(08:00 \pm 60 \text{ min})$  and  $20:00 \pm 60 \text{ min})$ . Re-educate the subject on diary completion and/or medication instillation procedures as needed.

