### 4.2. Treatment Period, Treatment Start Date, and Treatment End Date

This study has two study periods: Treatment Period and Treatment-free Follow-up Period. The start date and end date for each period are defined as follows in Table 3.

**Study Period Period Start Date Period End Date** The date at which a The date at which a subject takes the last dose of study Treatment Period randomized subject takes drug. If the date of the last dose is missing, the first dose of study drug The day of the Visit 6 (Month 2) date will be considered as the end date The day before the Study Exit date will be used for subjects who prematurely discontinued the study before Visit 6 (Month 2). If the Study Exit date of a non-completer is not available, then the day of the last available visit date will be considered the treatment. end date Treatment-free The day after the Visit 6 The date of Visit 7 (Month 3) Follow-up (Month 2) date. Period

 Table 3:
 Definitions for Period Start and End Dates by Study Period

*Treatment start date* and *Treatment end date* are the start date and the end date of the Treatment Period, defined in Table 3.

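### The SAP counts treatment-emergent AEs from the calendar date of first dose, the protocol from the dose itself, and the first dose is taken in the evening after the Day 1 visit

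*SAP*

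**What the plan says.** **SAP rule.** Under SAP 9.1.1 an AE is treatment-emergent "if the AE occurred on or after the treatment start date". The window closes 8 days after the treatment end date, with the last study visit given in brackets as an alternative end. SAP 4.2 says that the treatment start and end dates "are the start date and the end date of the Treatment Period, defined in Table 3". Table 3 sets the start as the date of the first dose. It is a date, with no clock time.

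**Protocol rule.** Protocol 8.3.1 says the analysis will summarize "those AEs that began or worsened in severity after the first IP administration".

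**First dose.** The footnote to SAP Figure 1 says: "On Day 1, subject should administer 1 dose of assigned medication after study visit", at 20:00 ± 60 min. The diary footnote to SAP Table 2 agrees: "Dosing for randomized subjects on Visit 2 (Day 1/Baseline) is after the study visit in the evening". The protocol synopsis gives the same time.

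**Collection and reporting.** Protocol 8.3.1 states: "All AEs will be collected from the signing of the Informed Consent Form (ICF) until subject withdrawal or the scheduled exit visit". The assessment schedule has an AE check at Visit 2, as well as slit lamp, IOP and ophthalmoscopy. SAP 9.1.1 sends only TEAEs to the tables, and SAP 9.2 lays these out by actual treatment received. Non-TEAEs are listed.

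**Declared changes.** For safety, SAP Section 10 reports only that pupil size and BCDVA were added. It does not mention the TEAE definition.

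**The concern.** A date rule does little harm where the first dose is given early in the baseline visit. Here the dose comes in the evening, after the visit is over. Most of Day 1, including the Visit 2 examinations, is untreated time that the SAP counts as treated.

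The SAP also treats Day 1 in two ways. Visit 2 is the Baseline Visit (SAP 4.1), and the Table 4 baseline window for most parameters includes Day 1. A slit-lamp finding made at Visit 2 is thus pre-treatment in the slit-lamp tables. The same finding, reported as an AE with that day's onset, is treatment-emergent in the AE tables.

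At stake is the accuracy of the by-arm AE tables, which serve the safety objective of comparison with placebo. With about 15 placebo subjects, one wrongly placed subject is visible. A second difference runs the other way. The SAP has no counterpart to the protocol's worsening limb, so an AE that began before dosing and became more severe on treatment could be left out.

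**Working it through.** The documents give no figure to reproduce. The check compares the two rules and then sizes the gap.

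**1. The rules side by side**

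| Event | SAP 9.1.1 | Protocol 8.3.1 |
|---|---|---|
| Onset before Day 1, no later worsening | Not TEAE | Not TEAE |
| Onset before Day 1, worsens after first dose | Not TEAE if the original onset date is kept | TEAE |
| Onset on Day 1 before the dose, no later worsening | **TEAE** | **Not TEAE** |
| Onset on Day 1 before the dose, worsens after it | TEAE | TEAE |
| Onset on Day 1 after the dose | TEAE | TEAE |
| Day missing, month and year of first dose | TEAE (SAP 5.2.3 imputes the first-dose date) | Timing unknown |

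The rules differ in rows 2 and 3. An AE recorded at Visit 2 with same-day onset belongs in row 3 or 4 whenever dosing follows the schedule.

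**2. Pre-dose share of Day 1** = dose hour / 24

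- 19:00: 19/24 = 79.2%
- 20:00: 20/24 = 83.3%
- 21:00: 21/24 = 87.5%

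**3. Pre-dose share of the whole TEAE window** = dose hour / (24 × (D + 8)). D is the number of treatment days, 57 to 63 from the Month 2 visit window, and 8 is the SAP's post-treatment allowance.

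- Smallest: 19 / (24 × 71) = 1.12%
- Central: 20 / (24 × 68) = 1.23%
- Largest: 21 / (24 × 65) = 1.35%

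**4. Weight of one subject**, planned arm sizes 15 and 30 (SAP 3.3): 1/15 = 6.7 points on placebo, 1/30 = 3.3 points on an active arm.

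**5. Chance of at least one such subject** = 1 − (1 − q)^n, where q is the probability that a subject has a pre-dose Day 1 AE. The documents do not give q, so the range is assumed.

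| q (assumed) | Placebo, n = 15 | Each active arm, n = 30 | Whole study, n = 75 |
|---|---|---|---|
| 0.5% | 7.2% | 14.0% | 31.3% |
| 1% | 14.0% | 26.0% | 52.9% |
| 2% | 26.1% | 45.5% | 78.0% |
| 5% | 53.7% | 78.5% | 97.9% |

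**6. Effect on the arm contrast.** Let p be the true post-dose incidence, and take pre-dose events as independent of later ones with the same q in every arm. The tabulated incidence is 1 − (1 − p)(1 − q) = p + q − pq. The difference between an active arm (A) and placebo (P) becomes (1 − q)(p_A − p_P). On average it shrinks by 1% of its size at q = 1% and by 5% at q = 5%.

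**The case against.** The strongest defence is that a date rule is a common, cautious choice when AE onset time is not recorded, and the documents do not show whether it is. The rule errs toward over-counting, in line with the SAP's imputation of partial onset dates to the first-dose date. Events before a drug is taken cannot depend on it, so randomization balances them in expectation. SAP Section 5 rules out testing of safety measures, so no test result can change. Investigators weigh the timing of an event against dosing when they rate causality (protocol 10.3.3), and drug reactions are tabulated separately, so a known pre-dose event should not appear as related.

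Most of this stands, and it limits the size of the problem. It does not remove the conflict. The SAP does not give caution as its reason. Its imputation rule covers unknown dates and does not justify counting events known to precede the dose. Causality ratings do not take an event out of the overall TEAE table.

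Two stronger readings are tempting, and the documents support neither:

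- **Pre-existing conditions enter the TEAE tables.** A known onset before Day 1 falls outside the SAP window. Only Day 1 onsets are affected.
- **Examination-related events on Day 1 materially inflate the rates on drug.** The documents give no rate of same-day AEs, dilation is required only at Screening and Exit, and 6.7 and 3.3 points are simply one subject's weight in an arm.

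**Conclusion.** The SAP and protocol define treatment-emergent AEs differently. If the SAP is followed as written, AEs known to precede the first dose enter the by-arm TEAE tables. Section 10 does not declare the difference.

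The expected effect is small and non-differential. It adds noise and slightly dilutes arm contrasts, and it favours no arm in expectation. The affected hours are most of Day 1 but only 1.12% to 1.35% of the TEAE window, and less if that window runs to the last study visit. Whether any subject is affected depends on a rate that the documents do not give. At an assumed 1% per subject, the chance of at least one is 14% on placebo and 26% in each active arm.

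The conclusion assumes that subjects took the first dose at the scheduled time. The missing worsening limb matters only if a worsening keeps its original onset date. If it is entered as a new AE, the date rule already captures it, and the documents do not say which applies.

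**What to change.** Align the start of the window in SAP 9.1.1 with the protocol: an AE is treatment-emergent if it began, or worsened in severity, after the first dose. For onsets on the date of first dose:

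- Class as non-TEAE only those that data already collected show to be pre-dose, either by onset time (if recorded) or because the event was documented at Visit 2, and that did not worsen after the dose.
- Keep as TEAE every Day 1 event of unknown timing, including those whose date was imputed to Day 1.
- Show the excluded events in the non-TEAE listing already planned in SAP 9.2.

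If the sponsor prefers the date rule, SAP Section 10 should declare it as a change from protocol 8.3.1 and give the reason.

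**Cost.** A few sentences in the SAP and one derivation rule. A new eCRF field should not be relied on, because the masked disposition review in SAP 10.2 shows that data collection was under way. The sponsor must check whether the AE data hold an onset time or show what was documented at Visit 2. If the SAP is already final, its introduction requires a deviation to be justified and documented in the study report.

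**Downside.** A pre-dose Day 1 event first reported at a later visit, with no onset time, will still count as TEAE, so the correction is partial.
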